4.1 Primary

To determine tolerability and safety profile of 2 different dosing schedule of single agent panobinostat maintenance therapy for a maximum of 12 intended cycles after autologous HCT in patients with multiple myeloma. We will calculate relative dose intensity (RDI) for each cohort.

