7.4.1 Dose reduction for panobinostat

This is an open-label trial to determine the safety and tolerability of single agent panobinostat (2 dosing schedules) as maintenance therapy after autologous HCT in patients with multiple myeloma. Patients will receive either 20 mg PO TIW, every other week, every 28-days (Cohort A) or 10 mg po daily x 7 days, every other week, every 4 weeks (Cohort B). If no grade 3 or 4 toxicities occur after completing a 28-day cycle of panobinostat maintenance therapy, and all non-hematologic toxicities improved to grade 1 or better, then the next cycle of panobinostat will be initiated as long as the minimal hematologic parameters are met (ANC $\geq 1 \times 10^9/L$; hemoglobin ≥ 8 g/dl; platelets $50 \times 10^9/L$) prior to each cycle. If a subject experiences toxicity, the dose of panobinostat will be reduced to one level lower (Table 7-1) and maintained at this level for all subsequent cycles unless further toxicities occur. Panobinostat dose modifications will be made according to the toxicity grading. Once a subject's dose of panobinostat is reduced, then that dose will be the maximal dose administered. The provisional dose levels of panobinostat (LBH589) to be investigated in this study are described in Table 7-1.

Table 7-1 Provisional dose reduction for panobinostat (LBH589)

Dose level#	Panobinostat oral dose	
	Cohort A (TIW, every other week, every 4 weeks)	Cohort B (Daily x 7 days, every other week, every 4 weeks)
1 (starting dose level)	20 mg	10 mg
-1	15 mg	10 mg on days 1, 3, 5, and 7

7.4.2 Dose modifications for study drug-related toxicity (see section 7.4.3 for dose modifications for prolonged QTc):

The criteria for dose modifications for study drug-related toxicity are detailed in [Table 7-2](#).

Table 7-2 Criteria for dosing delays, dose-reductions, and re-initiation of treatment due to study drug-related toxicity (excluding QT prolongation)

Worst Toxicity CTCAE Grade* unless otherwise specified (Value)	Dose Modification Guidelines At any time during a cycle of therapy (including intended day of dosing)	
HEMATOLOGICAL TOXICITIES		
Thrombocytopenia	Grade 3 (<50 and $\geq 25 \times 10^9/L$) with bleeding and Grade 4 (< $25 \times 10^9/L$)	Temporarily discontinue panobinostat dosing until resolved to \leq grade 2, or baseline, then, restart panobinostat at reduced level as per Table 7-1

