8.1 Visit schedule

Table 8-1 Evaluation and visit schedule

	Pre-HCT (Screening, not required)	Prior to maintenance (Enrollment: +45 to +180) [§]	Cycle #1 (start between +90 and +180)	Cycle #2****	Cycle #3****	Cycle #4****	Cycle #5****	Cycle #6****	Cycle #7****	Cycle #8****	Cycle #9****	Cycle #10*** *	Cycle #11*** *	Cycle #12*** *	End of study visit (4 weeks (± 14 days) follow up after the first dose of cycle #12)
Consent	X ⁺	X													
Enrollment		X													
H&P (SOC)		X	X ^{SS§}	X	X	X	X	X	X	X	X	X	X	X	X
Concomitant medications		X													
Toxicity (adverse event (AE)) assessment ^{SS}			X	X	X	X	X	X	X	X	X	X	X	X	X
Vital signs (SOC)		X ⁺⁺	X	X	X	X	X	X	X	X	X	X	X	X	X
EKG		X	X [*]	X ^{**}	X ^{**}	X ^{**}									
CBC and CMP (SOC)		X	X ^{***}	X ^{***}	X	X	X	X	X	X	X	X	X	X	X
PT/INR/PTT		X			X			X							X
LDH, cholesterol panel, GGT, uric acid		X													
Urinalysis		X													X
TSH, free T4		X													X
Serum pregnancy test ⁺⁺⁺		X	X	X	X	X	X	X	X	X	X	X	X	X	
SPEP, UPEP and serum free		X			X			X			X			X	

Confidential

light chains (SOC)															
Pneumococcal-13 conjugate vaccine (at around day +90 – SOC)		X [#]													
Peripheral blood research samples	X	X	X ^{****}	X	X			X			X				X
Bone marrow research samples	X [@]	X													X
Stem cell graft research samples	X														

*Single 12 lead EKG will be performed for pre-dose and 3 hours (± 15 minutes) post-dose on days 1 and 5 of cycle 1. A total of 4 EKGs during cycle 1 will be performed.
 **Single 12 lead EKG will be performed for pre-dose on day 1 of cycle 2 and beyond at each cycle (at least through cycle 4). If no significant QTcF prolongation is noted during the first cycle, then QTc monitoring is no longer required beyond cycle 4 (and may be performed at the investigator’s discretion). One EKG per cycle from cycle 2 to 4 (minimum).
 ***CBC to be performed weekly during cycle #1 and #2. CBC/CMP will also be performed on day 5 of cycle 1.
 ****Window to start cycles #2 to #12 would be ±7 days from the planned first day of each cycle.
 + Screening consent for research samples (bone marrow, peripheral blood and stem cell graft)
 ++ Height will be measured at screening visit prior to starting panobinostat maintenance therapy
 +++ Only for women of child bearing potential
 ++++ Peripheral blood research samples will be also collected on day 5 of cycle 1.

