13.1 Statistical methods and data analysis

This is an open label study of 2 different panobinostat maintenance dosing schedules after autologous HCT in patients with multiple myeloma. There are 2 cohorts and patients will be enrolled sequentially to cohort A, then to cohort B. The sample size is 30 patients for this trial (15 for each cohort). We expect that at least 2/3 of each cohort will complete 12 cycles of maintenance panobinostat (regardless of dose modification) and will be evaluable for the primary endpoint. The widths of 95% confidence interval (CI) are 0.356, 0.438, 0.487, 0.514, and 0.522 when the proportions of patients tolerating 12 cycles of maintenance are 0.9, 0.8, 0.7, 0.6, and 0.5, respectively.

A patient who withdraws from the study due to reasons other than death, disease progression or toxicity will be replaced and is considered as non-evaluable for primary endpoint. The proportion of patients tolerating the therapy will be reported with 95% CI. All 30 patients are eligible for secondary endpoints. We will compute the overall response rates before the transplant, after autologous HCT, and after the completion of maintenance therapy, and at best response. The OS and PFS will be estimated using the Kaplan-Meier method. We will also report the incidences of all grades and grade ≥ 3 toxicities. The two-sided 95% CIs for

proportion, and OS and PFS will be computed using the Clopper-Pearson method and the Greenwood formula, respectively. In addition, the frequency of B cell precursor as well as other cell subsets, and their 95% CI will be evaluated using t-distribution. If data do not meet normality assumption, the power transformation (e.g., log-transformation) will be conducted. Those patients who are not in CR before the transplant would be most suitable for T-effector activity analysis. This will be examined by the paired t-test or the Wilcoxon signed-rank test, depending on the data distribution.

Relative dose intensity (RDI) represents the ratio of the amount of a drug actually delivered [actual dose intensity (DI)] to the amount planned (planned DI). The purpose of calculating RDI is to evaluate whether the planned DI of a chemotherapy treatment was actually achieved which may suggest the feasibility of planned treatment regimen. There are multitude of reports demonstrating a correlation between RDI and survival in cancer treatment.

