$$\text{RDI} = (\text{total dose received by the patient} = \text{mg}) / (\text{planned full dose of drug} = \text{mg})$$

Optimal RDI for maintenance therapy in multiple myeloma has not been fully defined though it would be a surrogate measure for treatment feasibility. We intend to calculate RDI on two cohorts both together and separately. Missed doses, dose reduction and dose delay will be reportedly per cohort. The investigator will review the tolerability as a whole for 2 different cohorts and report feasibility of each cohort.

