13.1.3 Primary objective and hypothesis

The primary objective of this study is to determine the tolerability and safety profile of 2 different dosing schedules of single agent panobinostat maintenance therapy for a maximum of 12 cycles after autologous HCT in patients with chemosensitive multiple myeloma. We hypothesize that at least two-thirds of patients will be able to complete 12 cycles of intended maintenance therapy. The completion rate of 12 cycles of maintenance therapy in 15

evaluable patients will be reported along with 95% confidence intervals using the exact binomial distribution. We plan to calculate RDI for each cohort.

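### RDI is meant to show whether planned dose intensity was achieved, but its formula has no time term, so full-dose cycles given late still score 100%

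*Combined protocol and SAP*

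**What the plan says.** RDI stands beside the primary objective in section 4.1 ("We will calculate relative dose intensity (RDI) for each cohort") and again in section 13.1.3 ("We plan to calculate RDI for each cohort"). Section 13.1 gives its aim: "The purpose of calculating RDI is to evaluate whether the planned DI of a chemotherapy treatment was actually achieved". It describes RDI in words as "the ratio of the amount of a drug actually delivered [actual dose intensity (DI)] to the amount planned (planned DI"), so dose intensity is used there as a label for an amount. The formula that follows is total mg received over "planned full dose of drug", also in mg.

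The same section treats RDI as a stand-in for feasibility, to be calculated per cohort and pooled. It adds: "Missed doses, dose reduction and dose delay will be reportedly per cohort". Treatment is limited by number of cycles (12, planned as 48 weeks: sections 3, 7.1 and 7.3).

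**The concern.** Dose intensity is dose per unit of time. A ratio of milligrams to milligrams cannot show whether the planned rate was kept; it shows only what share of the planned total was given. If one schedule is completed only with repeated waits for blood counts and the other on time, both can report the same RDI. A reader who takes section 13.1 at its word would read 100% as delivery at the planned intensity. What is at stake is the interpretation of a descriptive feasibility measure for two schedules.

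**Working it through.** **1. Planned dose.** Section 3 gives 60 mg per week (A) and 70 mg per week (B). These reproduce as amounts per dosing week: 20 mg × 3 = 60 and 10 mg × 7 = 70. Dosing is every other week, so a 28-day cycle has two dosing weeks:

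- A: 60 × 2 = 120 mg per cycle; 120/4 = 30 mg/week on average; 120 × 12 = 1440 mg.
- B: 70 × 2 = 140 mg per cycle; 140/4 = 35 mg/week on average; 140 × 12 = 1680 mg.

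**2. What the formula registers.** Reductions lower it. At dose level -1 throughout (Table 7-1), A gives 15 × 3 × 2 = 90 mg per cycle, 90/120 = 0.75, and B gives 10 × 4 × 2 = 80 mg per cycle, 80/140 = 0.57. Missed doses that are not made up (section 7.1), doses omitted for QTcF (Table 7-3) and a skipped cycle (11/12 = 0.92) lower it too. Time does not enter.

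**3. Where full-dose delay can arise.**

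- Start window, section 8.1: "Window to start cycles #2 to #12 would be ±7 days from the planned first day of each cycle".
- Blood-count condition, section 7.4.1: "then the next cycle of panobinostat will be initiated as long as the minimal hematologic parameters are met". Platelets of 25 to <50 × 10⁹/L without bleeding, or ANC of 0.5 to <1.0 × 10⁹/L without fever, fall below the stated minimum but are not reduction triggers in Table 7-2. A general sentence in section 7.4.1 can be read as reducing the dose after any toxicity. The two passages should be reconciled. If the dose is reduced, the ratio registers the reduction but still not the delay.
- Delay limit, section 7.4.5: discontinuation after a delay of more than 28 days, with an exception for patients clearly benefiting. Holds for QTcF are limited to 7 days (section 7.4.3).

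**4. Twelve full cycles with d weeks of total delay.** Plan's formula: 1440/1440 or 1680/1680 = 1.00 for every d. Time-based RDI: (planned mg/(48 + d))/(planned mg/48) = 48/(48 + d), the same in both cohorts.

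| Total delay | Plan's formula | Time-based RDI | A, mg/week | B, mg/week |
|---|---|---|---|---|
| None | 100% | 48/48 = 100% | 30.0 | 35.0 |
| 1 week | 100% | 48/49 = 98% | 29.4 | 34.3 |
| One 28-day delay | 100% | 48/52 = 92% | 27.7 | 32.3 |
| 11 weeks (extreme) | 100% | 48/59 = 81% | 24.4 | 28.5 |

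The last row needs each of cycles 2 to 12 to start 7 days late, with the window counted from the previous cycle. Section 8.1 does not say how the planned first day is counted. On a fixed calendar, starts at the late edge of the window cost one week in total, which is the 98% row.

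**5. The opposite direction.** A patient who stops after one on-time cycle scores 1/12 = 8% on the cumulative ratio (12-cycle denominator) but 100% on a time-based ratio. Neither measure is sufficient alone.

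**The case against.** The strongest reply is that formula and verbal definition agree: section 13.1 speaks of amounts and then divides amounts, so the conflict is only with the name. That is true of the definition. It does not meet the purpose stated beside it, which concerns intensity.

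Second, dose delay is to be reported per cohort. A reader might infer that the plan hides delays; it does not. They are missing from the RDI value, not from the analysis. This limits the harm but does not make a 100% RDI mean that the planned intensity was achieved.

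Third, if dose were counted only to week 48, one 28-day delay would give 11/12 = 0.917, close to the time-based 0.923. The documents equate 12 cycles with 48 weeks as a plan, but state no calendar cut-off for dosing or for counting dose.

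Fourth, pure full-dose delay may be uncommon if most count-driven delays also lead to reduction. The documents do not settle this. Only the start window allows full-dose delay with no toxicity reading at all.

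Fifth, cumulative dose is itself a sound feasibility measure, because it registers early stopping. This stands, and the ratio should be kept.

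**Conclusion.** The point holds and is minor. As written, RDI is a relative cumulative dose and cannot show whether planned dose intensity was achieved. The gap is 2 percentage points for one week of total delay and 8 for one 28-day delay. The 81% figure is an extreme bound, not an expected value. These results assume full dose in all 12 cycles and dose counted past week 48; delay frequency is unknown.

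Two stronger readings are not supported. One is that the primary conclusion is compromised: the primary hypothesis in section 13.1.3 concerns completion of 12 cycles, and the accrual suspension criteria in section 13.1.5 use completion and toxicity rates, not RDI. The other is that any delay up to 28 days is tolerated and any longer one ends treatment: QTcF holds have their own 7-day limit, and section 7.4.5 allows an exception beyond 28 days.

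**What to change.** 1. Rename the existing ratio *relative cumulative dose* and state its denominator as the 12 planned cycles: 1440 mg (A), 1680 mg (B). As worded, a patient who stops after 6 full cycles scores 50% or 100%, depending on whether the denominator is 12 cycles or cycles started.
2. Add a time-based RDI per patient = (mg received / actual weeks) / (30 mg/week in A or 35 mg/week in B). Actual weeks run from first dose to the later of the end of the last cycle started and the date of permanent discontinuation. A hold that ends treatment is then counted: three full cycles followed by a 4-week hold give 12/16 = 75%, where a clock stopping at the end of cycle 3 would give 100%.
3. Always report both, per cohort and pooled, with the discontinuation reasons already recorded under section 7.4.4.

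The cost is wording in section 13.1 and one extra descriptive line per cohort. Dosages, dose changes, interruptions and visit intervals are already recorded (sections 7.1, 7.4 and 7.6); the date of permanent discontinuation must be available too. Values will be lower for patients with delays and can slightly exceed 100% if cycles start early (one week early in total: 48/47 = 102%). Time-based RDI does not register early stopping, so it must not be shown alone. No dose or clinical rule changes.

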13.1.1 Populations for analysis

This is an open-label, panobinostat maintenance therapy trial evaluating 2 different dosing schedules after autologous HCT in patients with multiple myeloma. Eligible patients have histologically confirmed multiple myeloma and have chemosensitive disease prior to starting the maintenance therapy. Fifteen patients per cohort will be enrolled and a total of 30 patients will be on this study.

13.1.2 Patient demographics/other baseline characteristics

Standard patient demographics and baseline disease characteristics will be collected: age, gender, immunophenotype, Durie-Salmon staging system, International Staging System, albumin, beta-2 microglobulin, myeloma risk stratification (high versus standard), prior systemic therapy, number of prior therapy, chemotherapy conditioning regimen and dose, and stem cell dose. Results will be tabulated.

13.1.3 Primary objective and hypothesis

The primary objective of this study is to determine the tolerability and safety profile of 2 different dosing schedules of single agent panobinostat maintenance therapy for a maximum of 12 cycles after autologous HCT in patients with chemosensitive multiple myeloma. We hypothesize that at least two-thirds of patients will be able to complete 12 cycles of intended maintenance therapy. The completion rate of 12 cycles of maintenance therapy in 15

evaluable patients will be reported along with 95% confidence intervals using the exact binomial distribution. We plan to calculate RDI for each cohort.

13.1.4 Secondary objective and hypothesis

The secondary objectives of the study are to evaluate following parameters in patients who receive panobinostat maintenance therapy after autologous HCT: overall response rate, best response rate, 2-year PFS and 2-year OS. The exploratory secondary objectives include evaluation of minimal residual disease, frequency of B cell precursors and immune subsets, protein acetylation, and immune response against pneumococcal vaccines and CRM. The association of minimal residual disease, B cell precursors, and immune response with response, PFS and OS will be evaluated using the Cox proportional hazards regression model.

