1.1 Overview of Maintenance Therapy in Multiple Myeloma

1.1.1 Myeloma maintenance therapy after transplant

Multiple myeloma is an incurable plasma cell malignancy despite recent advances in therapy with novel agents including lenalidomide and bortezomib.^{1,2} High-dose melphalan followed by autologous hematopoietic cell transplantation (HCT) offers progression-free survival (PFS) and overall survival (OS) benefits when compared to conventional chemotherapy.³⁻⁵ Recent phase 3 trials of lenalidomide maintenance post-autologous HCT demonstrated significant increase in PFS.^{6,7} In the Cancer and Leukemia Group B (CALGB) 100104 study (Table 1-1), 462 multiple myeloma patients were randomized to lenalidomide 10 mg daily or placebo after single autologous HCT.⁶ The median time to progression (TTP) was 46 months for the lenalidomide arm and 27 months for the placebo arm ($P < .001$). At a median follow-up of 34 months, the 3-year OS rates were 88% for the lenalidomide arm and 80% for the placebo arm ($P = .028$).⁶ A total of 23 out of 231 patients (10%) on lenalidomide arm discontinued maintenance due to adverse events. Hematologic adverse events were more common in lenalidomide group as well as grade 3 non-hematologic adverse events compared to the placebo group. In the Intergroupe Francophone du Myélome (IFM) 05-02 study (Table 1-1), 605 myeloma patients were randomized to lenalidomide 10 mg daily versus placebo until disease progression after single or tandem autologous HCT.⁷ The median PFS was 41 months for the lenalidomide arm and 23 months for the placebo arm ($P < .001$). The OS was 74% for the lenalidomide arm and 76% for the placebo arm ($P = .7$) at a median follow-up of 45 months.⁷ A total of 83 patients (27%) discontinued lenalidomide due to adverse events. Any Seventy-four percent of patients in the lenalidomide group experienced any grade 3-4 adverse events and hematologic was the most common adverse events. Approximately one third of patients experienced grade 3-4 non-hematologic adverse events.

Table 1-1. Lenalidomide maintenance therapy after autologous HCT

Study	N	Outcomes	
		Maintenance	No Maintenance
CALGB 100104 (McCarthy et al.) ⁶	460	
 • Median TTP 46 months • 3-yr PFS 66% • Median EFS 43 months • 3-yr OS 88% 	
 • Median TTP 27 months ($P < .001$) • 3-yr PFS 39% ($P < .001$) • Median EFS 27 months ($P < .001$) • 3-yr OS 80%

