IFM 05-02 (Attal et al.) ⁷	614	
 • Median PFS 41 months • 4-yr PFS 43% • Median EFS 40 months • 4-yr OS 73% 	
 • Median PFS 23 months ($P < .001$) • 4-yr PFS 22% ($P < .001$) • Median EFS 23 months ($P < .001$) • 4-yr OS 75%

Abbreviations: EFS, event-free survival

There have been extensive studies evaluating other maintenance options including thalidomide and bortezomib (Tables 1-2 and 1-3).⁸⁻¹⁸ Maintenance therapy can be associated with significant side effects such as constipation, fatigue, drug rash, cytopenias, peripheral neuropathy and thromboembolic events. Due to the complexity of potential side effects, these

choices may pose significant challenges to clinicians. As for lenalidomide, an increased incidence of second primary malignancies has been associated with its use.^{6,7,19} Despite PFS and OS benefits shown in some studies, no single therapeutic agent has been established as the widely agreed-upon standard for maintenance therapy after autologous HCT in multiple myeloma. As was described by the International Myeloma Working Group (IMWG) consensus statement on maintenance therapy, maintenance treatment decisions for individual patients must balance potential benefits and risks carefully.²⁰

Table 1-2. Thalidomide maintenance therapy after autologous HCT

Study	N	Outcomes	
		Maintenance	No Maintenance
IFM 99 (Attal et al.) ⁹	597	
 • 3-yr EFS 52% • 4-yr OS 87% 	
 • 3-yr EFS 37% ($P < .009$) • 4-yr OS 75% ($P < .04$)
Total Therapy 2 (Barlogie et al.) ¹⁰	668	
 • 5-yr EFS 64% • 8-yr OS 57% 	
 • 5-yr EFS 43% ($P < .001$) • 8-yr OS 44% ($P = .09$)
HOVON-50 (Lokhorst, et al.) ¹¹	556	
 • Median EFS 43 months • Median OS 73 months 	
 • Median EFS 22 months ($P < .001$) • Median OS 60 months ($P = .77$)
Spencer et al. ^{13a}	243	
 • 3-yr PFS 42% • 3-yr OS 86% 	
 • 3-yr PFS 23% ($P < .001$) • 3-yr OS 75% ($P = .004$)
MRC IX (Morgan et al.) ^{12b}	820	
 • Median PFS 30 months • 3-yr OS 75% 	
 • Median PFS 23 months ($P = .003$) • 3-yr OS 80% ($P = .26$)

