4.2 Secondary

- To evaluate the complete response rate to panobinostat maintenance therapy after autologous HCT.
- To determine the 2-year PFS and OS of autologous HCT followed by panobinostat maintenance therapy in patients with multiple myeloma.
- **Exploratory secondary objectives:**
 - To evaluate histone acetylation (H3 and/or H4) of peripheral blood mononuclear cells
 - To isolate and identify clonotypic B cell progenitors in multiple myeloma patients from the bone marrow, peripheral blood and stem cell grafts.
 - To evaluate T-cell immune response against known myeloma tumor associated antigens while on panobinostat maintenance.
 - To evaluate humoral immunity against pneumococcal serotypes included in the standard of care heptavalent pneumococcal conjugate vaccine, and to assess cellular immune responses against CRM adjuvant found in the heptavalent pneumococcal conjugate vaccine.
 - To evaluate minimal residual disease (MRD) after autologous HCT followed by panobinostat maintenance therapy using flow cytometry
 - To evaluate MRD after autologous HCT followed by panobinostat maintenance therapy using multiplex PCR for CDR3 sequences

5 Overall study design

This is an open-label trial to determine the safety and tolerability of 2 different dosing schedules of single agent panobinostat maintenance therapy in patients with multiple myeloma who underwent high-dose melphalan followed by autologous HCT in patients with multiple myeloma. It is unknown whether the toxicity profile of panobinostat will be accentuated in patients after autologous HCT in the setting of maintenance therapy, hence the dose chosen for maintenance therapy is lower than MTD dosing or other phase 2 studies. There are 2 dosing schedules evaluated in this protocol in order to assess optimal tolerable schedule for panobinostat maintenance therapy after autologous HCT. As secondary

objectives, we will evaluate response after completion of treatment, and 2-year PFS and OS. As correlative studies, we plan to evaluate MRD, and to assess clonotypic B cells following an autologous HCT. We also plan to evaluate T effector immune response after autologous HCT while on panobinostat maintenance therapy.

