6.1.1 Patient population

Adult patients with multiple myeloma who received high-dose melphalan (from 140 mg/m² to 200 mg/m²) followed by autologous HCT are eligible. A total of 30 patients (15 for each maintenance cohort) will be enrolled to the study.

Potentially eligible patients will be approached prior to autologous HCT for an optional research sample collection (where peripheral blood, bone marrow including archived formalin-fixed paraffin embedded bone marrow clot, and stem cell graft will be obtained) using a screening consent. Enrollment to the panobinostat maintenance therapy will occur after autologous HCT.

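### Ordinary Cox models of OS on the correlative markers would rest on about 2 to 7 deaths in 30 patients: often non-finite for binary or post-maintenance markers, and otherwise too imprecise to inform

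*Combined protocol and SAP*

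**What the plan says.** Section 6.1.1 fixes the size: "A total of 30 patients (15 for each maintenance cohort) will be enrolled to the study". Section 13.1 adds "All 30 patients are eligible for secondary endpoints" and, for the survival endpoints, "The OS and PFS will be estimated using the Kaplan-Meier method". The only survival horizon given is in the objective in section 4.2: "To determine the 2-year PFS and OS of autologous HCT followed by panobinostat maintenance therapy in patients with multiple myeloma". No length of follow-up or data cut-off is stated.

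Section 13.1.4 then says: "The association of minimal residual disease, B cell precursors, and immune response with response, PFS and OS will be evaluated using the Cox proportional hazards". It lists the marker evaluations as exploratory secondary objectives. It does not say how each marker is coded, whether markers enter singly or together, from what time follow-up starts for markers sampled during or after treatment, or what is done when events are few.

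The markers are of mixed type. Section 9.2 gives a binary cut-off for the pneumococcal IgG response and a percentage for the CRM T-cell response. Section 13.1 treats B-cell precursors as a frequency. MRD coding is not stated. Tables 8-1 and 9-1 schedule on-study marrow before maintenance and at end of study; the text of section 9.3 also mentions cycle 6.

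**The concern.** A Cox hazard ratio draws its information from events, not patients. The sample size of 30 is justified only by the width of the confidence interval for the completion rate, and nobody has counted the deaths that the OS marker models would have. If one group of a binary marker has no deaths, the partial likelihood is monotone: the estimate runs to zero or infinity and the Wald interval has no meaning. If the estimate is finite but rests on two or three deaths, one patient can reverse its direction.

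The risk is greatest for the reading of most scientific interest, MRD after maintenance, because only deaths after that sample can contribute. What is at stake is whether a reported marker-survival association could mean anything, not the primary endpoint.

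**Working it through.** **1. The plan's own figure.** The stated 95% CI widths for the completion proportion (0.356, 0.438, 0.487, 0.514, 0.522) reproduce to three decimals as Clopper-Pearson widths with n = 15 and x = 15p. They support the primary endpoint only. The documents contain no event count for OS or PFS to reproduce.

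**2. Deaths by 2 years.** Inputs: n = 30 and the OS figures in section 1.1.1 and Tables 1-1 to 1-3. Assumptions: constant hazard, everyone followed for 2 years. With survival S at t years, deaths = 30 × (1 − S^(2/t)).

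| Cited OS figure | 2-year OS | Deaths in 30 |
|---|---|---|
| 88% at 3 years (CALGB 100104, lenalidomide) | 0.918 | 2.45 |
| 80% at 3 years (CALGB 100104, placebo) | 0.862 | 4.15 |
| 73% at 4 years (IFM 05-02, lenalidomide) | 0.854 | 4.37 |
| 75% at 4 years (IFM 05-02, no maintenance) | 0.866 | 4.02 |
| 87% at 4 years (IFM 99, thalidomide; fewest deaths) | 0.933 | 2.02 |
| 55% at 5 years (HOVON-65, no maintenance) | 0.787 | 6.38 |
| Median 60 months (HOVON-50, no maintenance; most deaths) | 0.758 | 7.26 |

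The first two rows come from "the 3-year OS rates were 88% for the lenalidomide arm and 80% for the placebo arm" and the last from "Median OS 60 months".

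**3. Deaths after an end-of-maintenance marker.** Section 13.1.3 says "We hypothesize that at least two-thirds of patients will be able to complete 12 cycles of intended maintenance therapy", which gives 20 of 30. Maintenance lasts 48 weeks, leaving 2 − 48/52.18 = 1.08 years. Deaths = 20 × (1 − exp(−1.08h)), with h = −ln(S)/t per year. For 88% and 80% at 3 years, h = 0.0426 and 0.0744, giving 0.90 and 1.54. Over all cited figures the range is 0.74 to 2.78. If the 2 years run from transplant with a day +90 start, these numbers are lower.

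**4. Chance of no finite hazard ratio, binary marker.** For two equal groups, no true effect and survival probability s over the window, the chance that at least one group has no deaths is 2s^(n/2) − s^n.

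- Baseline marker, n = 30: 48% (88% at 3 years), 20% (80% at 3 years). Over all cited figures: 58% down to 3%.
- Post-maintenance marker, n = 20: 86% and 70%. Over all cited figures: 90% down to 40%.

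Simulation (20,000 runs per scenario, marker prevalence 0.5 or 0.3, true hazard ratio 1 or 2) gave 49-58% and 23-31% at baseline, and 87-89% and 71-76% after maintenance, for the 88% and 80% figures.

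**5. Continuous marker.** The same simulation (hazard ratio 1 or 2 per SD) gave 9-11% and 2-3% at baseline, and under 1% with 55% at 5 years. After maintenance it gave 44-47% and 24-28%, mostly because nobody dies, and 9-13% with 55% at 5 years.

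**6. Precision when the estimate is finite.** For a 50/50 marker and d deaths, the best-case SE of log HR is 2/√d, and the 95% CI multiplies and divides the HR by exp(1.96 × SE).

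| Deaths | SE | CI factor | Power, HR 2 | Power, HR 3 |
|---|---|---|---|---|
| 2 | 1.41 | 16 | 7% | 12% |
| 4 | 1.00 | 7.1 | 10% | 20% |
| 7 | 0.76 | 4.4 | 15% | 31% |

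Eighty per cent power needs 4 × (1.96 + 0.8416)²/(ln HR)² deaths: 66 for HR 2 and 27 for HR 3. A 50/50 marker has SD 0.5, so its contrast spans two SDs. Per SD of a continuous marker, the CI factor is about the square root of the value shown (about 4, 2.7 and 2.1).

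**7. PFS events by 2 years, lenalidomide trials.** From 3-year PFS of 66% and 39%: 7.3 and 14.0 events in 30. From 4-year PFS of 43% and 22%: 10.3 and 15.9. The IFM 05-02 medians of 41 and 23 months, through 30 × (1 − 2^(−24/m)), give 10.0 and 15.4. If three markers entered together, that would be about 2 to 5 events per marker.

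**The case against.** The strongest reply is that these analyses are exploratory. No sample size, test or decision depends on them, and the plan says so. That stands, and it limits how serious the point is. It does not make an ordinary partial-likelihood estimate usable when one group has no deaths.

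Three stronger readings are tempting, and the documents do not support them.

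- *That all the OS hazard ratios will often be infinite.* This holds for binary baseline markers on the lenalidomide figures and for many post-maintenance analyses. It does not hold for a continuous baseline marker such as B-cell precursor frequency, where the failure rate is 2-11% on the CALGB 100104 figures. Nor does it hold for a balanced binary baseline marker on the least favourable OS figure, where it is 3%. In those cases the trouble is imprecision.
- *That the plan implies 2 to 4 deaths.* The plan gives no number. That range comes from the lenalidomide trials alone; other cited figures reach about 7. Nor does the plan say that the Cox models censor at 2 years. Following all patients for 5 years would give 5.8 to 9.3 deaths on the CALGB 100104 figures, still in single digits.
- *That three markers will be fitted together to PFS.* Section 13.1.4 does not say so. It merely leaves the possibility open.

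It is also fair to say that a penalised OS estimate with a wide interval could be reported instead of dropping OS. The fix allows for that.

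**Conclusion.** The point holds as a matter of method for an exploratory analysis. On every OS figure the protocol cites, the OS marker models would rest on single-digit deaths by 2 years: about 2 to 7 in 30 patients, and about 1 to 3 after an end-of-maintenance marker. For a 50/50 post-maintenance marker, the chance of no finite hazard ratio is roughly 40-90%. For a binary baseline marker it is roughly 20-50% on the CALGB 100104 figures. Where the estimate is finite, the interval is too wide to separate a strong association from none. PFS can support one marker per model at most, and only imprecisely.

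The sizes rest on a constant hazard, 2-year follow-up, survival like that of the cited trials, two-thirds completion and, for the binary results, near-equal marker groups. MRD coding is unstated, so treating it as binary is an assumption. The primary endpoint is unaffected.

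**What to change.** Amend section 13.1.4 as follows.

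- Replace the OS marker models with a descriptive listing of deaths by marker status. If an OS hazard ratio is kept, make it a Firth-penalised estimate with a profile-likelihood 95% CI.
- For PFS, fit one marker per model by Firth-penalised Cox with profile-likelihood 95% CIs, or use an exact or permutation log-rank test for binary markers.
- State the coding of each marker.
- For markers measured during or after maintenance, start follow-up at the sampling time (landmark) and include only patients still at risk then.

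This changes SAP wording and uses standard software options. It needs no extra patients, samples or visits. The downside is that no conventional OS hazard ratio is reported.
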